## 8. STUDY ASSESSMENTS AND PROCEDURES

Before performing any study procedures, all potential subjects will sign an ICF as outlined in [Section 10.2](#).

All assessments and procedural details during Screening (Day -28 to Day -1), Pre-surgery/Surgery (Day 1), the Treatment Period (hours post end of surgery), and EOS/ET are described in the Schedule of Assessments ([Section 1.2](#)).

All efficacy, safety, and PK assessments are anchored to time at end of surgery (last suture).

Pharmacokinetic (PK) sampling timepoints correlate with the collection of the 11-pt Numeric Pain Rating Scale (NPRS) efficacy assessments when they overlap.

### 8.1. Efficacy Assessments

Study staff will record subject-reported pain assessments via a standard 11-point NPRS at the following time points post-end of surgery: 0, 1, 2, 3, 4, 6, 8, 10, 12, 16, 20, 24, 30, 36, 42, 48, 54, 60, 66, and 72 hours within a  $\pm 10$ -minute window ([Appendix C](#)). NPRS will be collected prior to PK sampling and administration of rescue medication.

Study staff will record subject-reported PGA of pain control using a 5-point scale (poor, fair, good, very good, excellent) at the following time points post-end of surgery: 24, 48, and 72 hours within a  $\pm 10$ -minute window and just prior to receiving a dose of rescue medication ([Appendix D](#)).

Study staff will record the time and the dose of rescue medication administered on the rescue medication form. NPRS and PK sampling will be collected immediately prior to administering rescue medication.

Nausea will be self-assessed using an 11-point NNRS at the following time points post-end of surgery: 1, 4, 8, 12, 24, 48, 72 hours within a  $\pm 10$ -minute window ([Appendix E](#)). Additional NNRS assessments will be collected when an AE of nausea or vomiting is reported or prior to any rescue antiemetic administration. Subject will report Sleep Interference Score (SIS) using an 11-point NRS scale (0-10) at 24, 48 and 72 hours post-end of surgery within a  $\pm 15$  minute window ([Appendix F](#))

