Secondary Endpoints:	
Key Secondary Endpoints:
 
 
SPI48: low dose XG005 vs placebo
 
Total tramadol rescue medication consumption in morphine equivalents (MEQs) over 48 hours: high dose XG005 vs placebo
 
Total tramadol rescue medication consumption in morphine equivalents (MEQs) over 48 hours: low dose XG005 vs placebo
 
 
Additional Endpoints:
 
 
Time to first use of rescue medication from end of surgery: high dose XG005 vs placebo
 
Time to first use of rescue medication from end of surgery: low dose XG005 vs placebo
 
PGA at 48 hours: high dose XG005 vs placebo
 
PGA at 48 hours: low dose XG005 vs placebo
 
Cumulative Nausea (NNRS) assessment scores through 24 hours: high dose XG005 vs placebo
 
Cumulative Nausea (NNRS) assessment scores through 24 hours: low dose XG005 vs placebo
 
SPI48: high dose XG005 vs low dose XG005
 

Tertiary Endpoints:	
Tertiary Endpoints for All Treatment Arms:
 
 
Total rescue medication consumption at 24, 48, and 72 hours
 

	
 
• Nausea (NNRS) assessment scores at 1, 4, 8, 12, 24, 48, and 72 hours
 
• SPI at 0, 1, 2, 3, 4, 6, 8, 10, 12, 16, 20, 24, 30, 36, 42, 48, 54, 60, 66, and 72 hours
 
• Pain intensity at various timepoints
 
• SIS at 24, 48 and 72 hours
 
• Percentage of subjects requiring rescue at various timepoints
 
• PGA of pain control at various timepoints
 
• Ramsay Sedation Scale at various timepoints
 
 
Exploratory:
 
 
• Estimate of subject susceptibility to placebo response at Screening using a pre-study personality questionnaire
 

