- o) Subjects will be permitted rescue medication throughout the 72-hour inpatient domiciling period as follows to manage breakthrough pain only if it occurs while domiciled: IV acetaminophen 1 g, will be administered Q 6 hours, PRN, up to 4 g in 24 hours. If a patient is unable to tolerate acetaminophen or if there is insufficient pain relief, 50 mg tramadol will be administered Q 4 hours, PRN, up to 300 mg in 24 hours. Study staff will record the time and the dose of rescue medication administered on the rescue medication form. NPRS and PK sampling will be collected immediately prior to administering rescue medication. Only the protocol-defined rescue medication is permitted in the study.
- p) Study staff will record subject-reported pain assessments via a standard 11-point NPRS at the following time points post-end of surgery: 0, 1, 2, 3, 4, 6, 8, 10, 12, 16, 20, 24, 30, 36, 42, 48, 54, 60, 66, and 72 hours within a  $\pm 10$ -minute window ([Appendix C](#)). NPRS will be collected prior to PK sampling and administration of rescue medication.
- q) Pain intensity assessments scheduled between 24:00 and 06:00 may be skipped if the subject is sleeping. However, consecutive pain assessments may not be skipped, and the Hour 12, Hour 24, and Hour 48 pain assessments must be completed even when they fall asleep between 24:00 and 06:00.
- r) Study staff will record subject-reported PGA of pain control using a 5-point scale (poor, fair, good, very good, excellent) at the following time points post-end of surgery: 24, 48, and 72 hours within a  $\pm 10$ -minute window and just prior to receiving a dose of rescue medication ([Appendix D](#)). PGA will also be performed and recorded at early termination.

- s) Nausea will be measured after the end of surgery by using the 11-point NNRS at the indicated time points with a  $\pm$  10-minute window ([Appendix E](#)). PK sampling blood draws will always be performed after NNRS assessment. Additional NNRS time points will be collected when an AE of nausea or vomiting is reported or prior to any rescue antiemetic medication. Administration of antiemetic medications are limited to subjects with active vomiting, subjects with a score  $\geq 5$  on the NNRS, or by subject request only. No pretreatment for potential nausea and vomiting is permitted.

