### 3. OBJECTIVES AND ENDPOINTS

Objectives	Endpoints
Primary Efficacy:	

 
To evaluate the efficacy of high dose XG005 [1250 mg Q12] compared to placebo for pain control in subjects undergoing bunionectomy.
 
	
 
Summed pain intensity from end of surgery to 48 hours post-surgery (SPI48) for high dose XG005 vs placebo
 

Secondary Efficacy:	

 
To evaluate the efficacy of low dose XG005 [750 mg Q12] compared to placebo for pain control in subjects undergoing bunionectomy.
 
To evaluate high and low dose XG005 compared to placebo for total rescue consumption and time to first use from end of surgery.
 
To evaluate high and low dose XG005 compared to placebo for PGA
 
To evaluate high and low dose XG005 compared to placebo for postoperative nausea.
 
To evaluate the efficacy of high dose XG005 compared to low dose XG005 for pain control in subjects undergoing bunionectomy
 
	
Key Secondary Endpoints:
 
 
SPI48: low dose XG005 vs placebo
 
Total tramadol rescue medication consumption in MEQs over 48 hours: high dose XG005 vs placebo
 
Total tramadol rescue medication consumption in MEQs over 48 hours: low dose XG005 vs placebo
 
 
Additional Analgesic Endpoints:
 
 
Time to first use of rescue medication from end of surgery: high dose XG005 vs placebo
 
Time to first use of rescue medication from end of surgery: low dose XG005 vs placebo
 
PGA at 48 hours: high dose XG005 vs placebo
 
PGA at 48 hours: low dose XG005 vs placebo
 
Cumulative nausea (NNRS) assessment scores through 24 hours: high dose XG005 vs placebo
 
Cumulative Nausea (NNRS) assessment scores through 24 hours: low dose XG005 vs placebo
 
SPI48: high dose XG005 vs low dose XG005
 

Tertiary Efficacy (All Treatment Arms):	

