### 6.2. Dosing and Administration

Study drug (XG005 low or high dose, or placebo) will be administered as an oral dose 60 minutes prior to surgery on Day 1 then every 12 hours for 72 hours after the time of first dose. The number and strength of active drug tablets to be administered at each dose level is shown in Table 1. Subjects randomized to placebo will receive the corresponding number of placebo tablets.

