### 9.3. Multiplicity Adjustment

A serial gatekeeping procedure will be used to control the overall type-1 error rate at 0.05 for primary and secondary endpoints. If the primary endpoint is not significant at a two-tailed alpha of 0.05, there is no testing on secondary endpoints. If the primary endpoint is significant at a two-tailed alpha of 0.05, the secondary endpoints will be tested following the hierarchy testing procedure with a pre-specified order as Section 3. If any secondary endpoint is not significant, the successive secondary endpoints will not be tested.

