**APPENDIX E:      NUMERIC NAUSEA RATING SCALE**

**On a scale of 0-10, please rate your nausea by marking an “X” in the appropriate box that best describes your nausea level NOW.**

 0	 1	 2	 3	 4	 5	 6	 7	 8	 9	 10
No nausea										Worst nausea imaginable

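### Cumulative nausea through 24 h has no scheduled rating between hours 12 and 24, and the plan does not say whether event-triggered ratings count towards the score

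*Combined protocol and SAP*

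**What the plan says.** Section 8.1 schedules nausea as follows: "Nausea will be self-assessed using an 11-point NNRS at the following time points post-end of surgery: 1, 4, 8, 12, 24, 48, 72 hours". Appendix E asks for the box that "best describes your nausea level NOW", so a rating does not look back. The sentence after the schedule adds unscheduled ratings: "Additional NNRS assessments will be collected when an AE of nausea or vomiting is reported or prior to any rescue antiemetic administration". Footnote s of the Schedule of Assessments says the same.

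The Synopsis and Section 3 list the endpoint for each dose against placebo; the high-dose entry in Section 3 reads "Cumulative nausea (NNRS) assessment scores through 24 hours: high dose XG005 vs placebo". Counting three key and seven additional secondary endpoints, the two nausea comparisons are 8th and 9th of ten. Section 9.3 places them under error control: "A serial gatekeeping procedure will be used to control the overall type-1 error rate at 0.05 for primary and secondary endpoints".

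No section says whether the cumulative score is a sum or a time-weighted area, or whether triggered ratings enter it. Sections 9 and 9.5.2 leave such detail to a separate SAP, which is not in the text available here.

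Pain (NPRS) is scheduled at 16 and 20 h, and Section 8.2 puts the Ramsay sedation rating on the same time sequence.

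**The concern.** An endpoint described as cumulative over 24 hours has four scheduled ratings in the first 12 hours and one, at hour 24 itself, in the second 12. Because each rating refers only to that moment, the 24 h rating cannot recover an episode that came and went overnight. The gap contains the plasma peak of the second dose.

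The ratings that can occur in the gap depend on the outcome: they exist for subjects who report nausea or vomiting or who are about to receive an antiemetic. If they are left out of the score, the second half of the window rests on its two end points. If they are simply summed in, subjects with more triggered ratings accumulate higher scores partly because they were rated more often. At stake are the precision and interpretation of two formally tested comparisons. A SAP can settle the scoring, but it cannot supply ratings that were never taken.

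**Working it through.** **The plan's own figures.** The documents give no design figure for the nausea endpoint. The only one stated, 130 per arm for 90% power at a standardized effect of 0.40 (Section 9.2), reproduces: 130 per arm gives 89.7% by the normal approximation. It concerns SPI48 and does not bear on this point.

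**Coverage.** Scheduled times up to 24 h are 1, 4, 8, 12 and 24 h: five ratings. The longest gap is 24 - 12 = 12 h, which is 12/24 = 50% of the window. In a plain sum, 4/5 = 80% of the scheduled ratings come from the first 12 h.

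**Where dose 2 falls.** Dosing is "oral dose 60 minutes prior to surgery on Day 1 then every 12 hours for 72 hours", with a window of 10 min either side of the 60 (Synopsis). Surgery lasts at most 90 min (Section 6.5.5). No minimum is given, so 20 min is assumed. Tmax is about 4 h (Section 4.2).

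- Dose 2 after last suture = 12 h - (dose-to-surgery interval + surgery duration).
- Earliest: 12 - (70 + 90)/60 = 9.33 h. Latest: 12 - (50 + 20)/60 = 10.83 h.
- Adding 4 h puts the peak at 13.3-14.8 h. With the 10-minute window on dose 2 it is 13.2-15.0 h; with an assumed Tmax of 3-5 h and no dose 2 window it is 12.3-15.8 h. Every case lies between 12 and 24 h.

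**Weights if the score is a trapezoid area over 1-24 h.** An interior rating has weight (next time - previous time)/2; an end rating has half its adjacent interval. All are divided by 23 h.

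| Rating (h) | Current schedule | With 16 and 20 h |
|---|---|---|
| 1 | 1.5/23 = 6.5% | 6.5% |
| 4 | 3.5/23 = 15.2% | 15.2% |
| 8 | 4/23 = 17.4% | 17.4% |
| 12 | 8/23 = 34.8% | 4/23 = 17.4% |
| 16 | none | 17.4% |
| 20 | none | 17.4% |
| 24 | 6/23 = 26.1% | 2/23 = 8.7% |

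The 12 h and 24 h ratings together fall from 14/23 = 60.9% to 6/23 = 26.1%.

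**What one episode scores (assumed shape).** Take a triangular episode with peak score 6 lasting 6 h, so the true area is 18.0. Centred at 14.67 h, five ratings recover 5.3 and seven recover 16.0. Centred at 13.5 h, five ratings give 24.0 and seven give 16.0. The error with five ratings can go either way.

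**Precision (assumed model).** Let the within-subject correlation between times s and t be p + (1 - p)exp(-|s - t|/T), where p is the stable share of variance and T the time constant. With a the trapezoid weights, b uniform weights on a 0.1 h grid and C the covariance, the squared correlation with true mean nausea is (a'Cb)^2 / [(a'Ca)(b'Cb)], and the score variance is a'Ca.

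| T, p | Squared correlation now | With 16 and 20 h | 16 h skipped | Variance reduction (16 h skipped) |
|---|---|---|---|---|
| 2 h, 0% | 0.46 | 0.75 | 0.63 | 28% (15%) |
| 8 h, 0% | 0.87 | 0.97 | 0.94 | 3.0% (1.8%) |
| 2 h, 50% | 0.88 | 0.96 | 0.93 | 6.0% (3.2%) |
| 8 h, 50% | 0.96 | 0.99 | 0.98 | 1.0% (0.6%) |

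Intermediate time constants and p = 30% fall within these limits.

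**The case against.** **The gap is not empty.** A reader might infer that half the window is unmeasured. The documents do not support that: subjects are domiciled for at least 72 h after surgery, and any reported nausea or vomiting event or antiemetic use triggers a rating. What stands is that no rating is scheduled there and the triggered ones have no defined role.

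**The peak is of plasma concentration.** A reader might infer that peak nausea after dose 2 is missed. The documents give no time course for nausea, and the Phase 1 summaries in Section 2.3 do not name it among the notable events. They also do not show that anaesthetic nausea dominates the first 12 h or that overnight tramadol adds nausea. The timing argument shows only that the gap is not a pharmacologically quiet period.

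**The score is undefined.** It would go too far to say the endpoint cannot represent cumulative nausea. The 61% applies only if a trapezoid is chosen, and all arms share one schedule, so this is a matter of noise and coverage rather than demonstrated bias.

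**The gain may be small.** With slowly varying nausea or a large stable component, the variance reduction is about 1-3%. Footnote q allows pain ratings between 24:00 and 06:00 to be skipped during sleep. If surgery ends between 08:00 and 14:00 (assumed), hour 16 falls in that period, and losing it roughly halves the variance reduction. Section 2.3 reports somnolence in 7 of 24 (29%) XG005 subjects in the multiple-dose cohort, so skipping could differ by arm. The present 12 h and 24 h nausea times coincide with pain contacts that may not be skipped, which is a reasonable motive for the current grid. These points shrink the benefit without removing it: squared correlation rose in every scenario run, with or without the 16 h rating.

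**The endpoint ranks low.** The high-dose nausea comparison is tested only if the primary and seven earlier secondary endpoints succeed; the low-dose comparison needs one more success. This limits the consequence, and the primary analysis and sample size are untouched.

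**Conclusion.** The point holds as a modest, inexpensive improvement. Cumulative NNRS through 24 h rests on five scheduled momentary ratings, with none scheduled across half the window, and the plan leaves open whether the triggered ratings in that half count. The first half of that statement, and the 61% and 26% trapezoid weights, need no assumption beyond the choice of a trapezoid. The dose 2 timing rests on an assumed minimum surgery of 20 min. The precision figures (squared correlation from 0.46-0.96 to 0.75-0.99, variance 1-28% lower) rest on an assumed exponential correlation with time constant 2-8 h and 0-50% stable variance, for which the documents give no data.

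**What to change.** - Add NNRS at 16 and 20 h in the Synopsis, Section 8.1 and the Schedule of Assessments, at the contacts already planned for NPRS and the Ramsay scale. Apply footnote q's sleep-skip rule, including its bar on consecutive skips; hours 16 and 20 are adjacent, so a subject who follows the schedule keeps at least one of them.
- Define the 24 h score in the protocol and SAP as the time-weighted area over scheduled ratings.
- List triggered ratings separately and include them in a sensitivity analysis, so that an episode reported when the 16 h rating was skipped is not lost.
- Report skipped 16 and 20 h ratings by arm.

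The cost is two extra one-item ratings per subject plus schedule and SAP wording. The downside is some ratings missing through sleep, possibly unequally by arm. The schedule change has to precede data collection, because a momentary rating cannot be recovered afterwards; the scoring definition can follow in the SAP before database lock.

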### 8.2. Safety Assessments

The timing and frequency of all safety assessments are provided in the SOA ([Section 1.2](#)). Safety endpoints include monitoring and recording of AEs and SAEs, clinical laboratory results (serum chemistry, hematology, coagulation, and urinalysis), 12-lead ECG results, and vital signs measurements (blood pressure [systolic and diastolic], heart rate, respiratory rate, oral body temperature, and continuous pulse oximetry), and recording of relevant safety data.

Trained staff on hand in the research unit will monitor respiratory safety via respiration rate, continuous pulse oximetry and oxygen saturation ( $\text{SpO}_2$ ) checks every 12 hours post-end of surgery within a  $\pm 10$ -minute window, and somnolence if observed by Staff at times other than

when a formal assessment of somnolence is scheduled. The Ramsay Sedation Scale (RSS, [Appendix G](#)) will be used as an assessment of sedation (somnolence) with the same time sequence as the NPRS determination, but with a window of  $\pm 15$  minutes. A Columbia-Suicide Severity Rating Scale since last visit ([Appendix K](#)) will be administered at 72 hours post treatment and at the follow-up visit and at the end of study visit/early termination visit.

For all safety assessments, the investigator will determine whether results are clinically significant, which is defined as any variation in a result that has medical relevance and that may result in an alteration in medical care (e.g., active observation, diagnostic measures, or therapeutic measures). If clinical significance is noted, the result and reason for significance will be documented and an AE reported on the AE page of the subject's electronic case report form (eCRF). The investigator will monitor the subject until the result has reached the reference range or the result at Screening, or until the investigator determines that follow-up is no longer medically necessary.

### **8.2.1. Reporting Adverse Events and Serious Adverse Events**

The investigator is responsible for ensuring that all AEs and SAEs are recorded in the eCRF and reported to the sponsor, regardless of their relationship to study drug or clinical significance. If there is any doubt as to whether a clinical observation is an AE, the event should be reported.

#### **8.2.1.1. Definition of Adverse Events**

An adverse event (AE) is any untoward medical occurrence in a patient or clinical trial subject administered a pharmaceutical product, whether or not there is a causal relationship suspected between the product and the event. An AE can therefore be any unfavorable and unintended sign, symptom or disease that is temporally associated with the use of the pharmaceutical product.

An AE includes any untoward medical occurrence in a subject or clinical trial participant administered a pharmaceutical product, whether or not there is a causal relationship suspected between the product and the event. An AE can therefore be any unfavorable and unintended sign, symptom, or disease that is temporally associated with the use of the pharmaceutical product.

A treatment emergent adverse event (TEAE) is defined as any event that was not present before exposure to study drug or any event already present that worsens in intensity or frequency after exposure.

A suspected adverse reaction is any AE for which there is a reasonable possibility that the study drug caused the AE. For the purposes of investigational new drug safety reporting, "reasonable possibility" means that there is evidence to suggest a causal relationship between the study drug and the AE. A suspected adverse reaction implies a lesser degree of certainty about causality than an adverse reaction.

An adverse reaction is any AE caused by a study drug. Adverse reactions belong to a subset of all suspected adverse reactions and indicate that there are reasons to conclude that the study drug caused the event.

### 8.2.1.2. **Definition of Serious Adverse Event**

An AE or suspected adverse reaction is considered “serious” if, in the view of either the investigator or sponsor, it results in any of the following outcomes:

- Death
- Life-threatening AE (i.e., immediate risk of death from the event as it occurred; this does not include an AE that, had it occurred in a more serious form, might have caused death).
- Inpatient hospitalization or prolongation of existing hospitalization
- Persistent or significant disability/incapacitation
- Congenital anomaly

Important medical events that may not result in death, be life threatening, or require hospitalization may be considered serious when, based upon appropriate medical judgment, they may jeopardize the subject and may require medical or surgical intervention to prevent one of the outcomes listed in this definition. Examples of such medical events include allergic bronchospasm requiring intensive treatment in an emergency room or at home, blood dyscrasias or convulsions that do not result in inpatient hospitalization, or the development of drug dependency or drug abuse.

### 8.2.1.3. **Assessment of Severity**

The severity (or intensity) of an AE will be assessed based on FDA Guidance Toxicity Grading Scale for Healthy Adult and Adolescent Volunteers Enrolled in Preventive Vaccine Clinical Trials ([Appendix L](#)). The investigator will assess the intensity of each AE/SAE based on his/her clinical judgment.

An AE that is assessed as severe should not be confused with an SAE. Severity is a category utilized for rating the intensity of an event; both AEs and SAEs can be assessed as severe.

Changes in the severity of an AE should be documented to allow the duration of the event at each level of intensity to be assessed. An AE characterized as intermittent does not require documentation of the onset and duration of each episode.

